2.2.4 Clinical Efficacy of AZD2171 in ASPS

Efficacy and tolerability data were collected for 7 patients with ASPS (ages 26–49 years) treated with AZD2171; one patient was treated in a Phase II randomized trial of AZD2171 with or without prophylactic antihypertensive therapy, and 6 patients were treated in a Phase II study in patients with imatinib-refractory gastrointestinal stromal tumours (GIST) or other soft tissue sarcoma. AZD2171 was administered orally once daily at an initial dose of 45 mg/day. Four patients had confirmed partial responses that have lasted for 169, 198, 226, and 352 days, respectively. Three patients have had prolonged disease stabilization lasting longer than 200 days. These data demonstrate an exciting activity profile for AZD2171 that supports further investigation in patients with ASPS (Figure 2).

[figure not shown]

Figure 2: Pre- and post-treatment CT scans from a young woman with ASPS in the axilla and lungs treated with AZD2171 from August 2006 to June 2008.

The most frequently reported adverse events in patients with ASPS were similar to those reported in the other studies [20, 26]: fatigue (n=6), diarrhea (n=5), stomatitis (n=4), headache (n=3), and hypertension (n=3) [27].

2.2.5 AZD2171 in Pediatric Patients With ASPS

AZD2171 has been studied in 16 children (ranging from 8 to 18 years of age, median 15 years) with refractory solid tumors, excluding primary brain tumors, in a recently reported clinical trial [28]. The MTD was determined to be 12 mg/m²/d (equivalent to 20 mg per dose based on a BSA of 1.8 m²). Objective responses were observed in several patients with sarcomas, including Ewing sarcoma, osteosarcoma, and synovial sarcoma. Of the 3 patients with ASPS, one had prolonged disease stabilization and received more than 15 cycles of therapy.

This study will allow pediatric patients with ASPS access to AZD2171 to determine the activity in children <16 years of age. AZD2171 will be administered to all pediatric subjects at the pediatric MTD, dosed according to a standardized dosing nomogram (Appendix H).

2.2.6 AZD2171 Clinical Toxicity

Based on evidence from animal data with AZD2171 (vascular and renal pathology) and results in the ongoing Phase I clinical studies, it is possible that the agent will produce hypertension in man. Because hypertension seen in animals has been abrogated by nifedipine, the change is thought to be mechanistically related to inhibition of VEGF signaling, although a direct toxicologic effect on the blood vessels and kidneys cannot be ruled out. The potential for hypertensive changes following AZD2171 administration is additionally supported by evidence from use of other antiangiogenic agents in the clinic. For these reasons, patients will be monitored frequently for changes in blood pressure and renal function (blood urea nitrogen, creatinine, and urinary protein).

Certain physiologic processes other than endothelial cell growth are dependent on VEGF signaling, so inhibition of that growth factor may have implications for use of AZD2171 in selected patient populations. AZD2171 interferes with normal reproductive processes and completely prevents fetal development in rats at a dose of 2.5 mg/kg/day. For this reason, women of childbearing potential should have a negative pregnancy test before treatment with AZD2171 is initiated. In rat studies, AZD2171 significantly inhibited endochondral ossification and corpora lutea formation [29].

DLTs in the pediatric population included nausea, vomiting, fatigue, hypertension and prolonged QT interval. Non-dose limiting toxicities included left ventricular dysfunction, elevated thyroid stimulating hormone, palmar-plantar erythrodysesthesia, weight loss, and headache [28]. Five out of 16 patients (30%) had non-dose limiting decreased left ventricular function (LVEF) during the first treatment cycle, and one patient had a grade 2 decrease in LVEF following cycle 2 [28]. In two patients, the LVEF improved within 4 weeks without intervention or dose modification.

Prior recommendations suggested that pediatric studies with AZD2171 be undertaken with caution because of the potential for increasing the zone of hypertrophy in the epiphyseal growth plates, thus preventing ossification during long bone growth. In the pediatric Phase I trial of AZD2171 [28], six patients had not achieved skeletal maturity at enrollment. In these patients, the median number of cycles administered was four (range, 2 to 15), and increase in height measured by triplicate stadiometer measurement during AZD2171 administration was 0.6 cm (range, 0 to 1.9 cm). No growth plate toxicity was identified in patients enrolled on this trial.

Pediatric patients in this study will be monitored closely for potential toxicity; in addition to adult monitoring parameters, height and weight analysis will be performed, and BSA calculations and frequent blood pressure evaluations will be monitored.

2.3 Rationale

There is no effective systemic treatment for patients with metastatic ASPS, but data from Phase II studies with AZD2171 supports further clinical investigation in patients with

metastatic ASPS[27]. Pediatric patients with ASPS will be enrolled to further evaluate clinical activity observed in the Phase I study of AZD2171 [28].

2.4 Trial Update

The results from this trial in adult patients with advanced ASPS were published in 2013 (Kummar et al. 2013). The objective response rate was 35% with 15 of 43 evaluable patients achieving a partial response (95% confidence interval: 21-51%) and 60% (26 patients) having a best response of stable disease. The disease control rate (partial response + stable disease) was 84% at 24 weeks. There were no responses in a 7-patient pediatric cohort of this study, for whom the best response was prolonged stable disease. This difference in response was considered potentially due to the maximum tolerated pediatric dose allowed being lower than the adult dose (Cohen et al. 2019). The protocol is closed to accrual. Two pediatric patients and one adult patient are continuing to receive cediranib after 59, 84, and 133 cycles, respectively.

2.5 Correlative Studies

Current knowledge of potential therapeutic targets and their expression pattern in ASPS is limited. Only a few studies of small sample size, using archival pre-treatment tissue, have demonstrated some potentially targetable angiogenic factors [4, 30] through identification of up-regulated angiogenesis genes such as *angiogenin*, *HIF1 α* , *TGF β 1*, *JAG1*, *midkine*, *c-MET*, and *VEGF*. Paired pre- and post-treatment tumor biopsies would be of significant benefit in the quest for new target identification. In addition, early data from Phase II studies with the VEGFR blocker AZD2171 in treating patients with ASPS, as well as our own data, merit further understanding of the mechanism of action of this therapeutic agent. A major limitation to the study of therapeutic targets in ASPS is the rarity of this tumor, making access to human specimens difficult. This study provides the rare opportunity to acquire tissue. Paired pre- and post-treatment tumor biopsies would be of significant benefit in providing insight into the mechanism of action of AZD2171 by allowing detection of gene alterations as a direct consequence of AZD2171 effect and by comparing findings between responders and non-responders.

Tumor biopsies are not mandatory for participation in this protocol. For those willing to undergo biopsies, pre-treatment biopsies will be collected at baseline, and to try to detect early drug effect, a second biopsy will be performed between D3 and D5 of treatment and subjected to gene expression profiling. The time point for the second biopsy has been selected to maximize the possibility that any transcriptional changes seen are due to a direct drug mechanism of action versus any inflammatory infiltrate- or other endpoint-related findings. A third optional biopsy after completion of 4 weeks of therapy (between C1D28 and C2D7) may be collected with the intention of providing further information about disease response to treatment. The timing of the biopsies may change depending on findings from gene analysis. However, the total number of biopsies per patient will not change.

2.6 CT Volumetric Density Assessment

The most widespread method of measuring metastatic tumor burden and treatment response in clinical trials, and the one used in this study (Section 11.1), is RECIST (Response Evaluation Criteria in Solid Tumors) [31]. RECIST uses 2D-proxies (single maximum diameter on axial images) to estimate tumor volumes. RECIST is limited in that it only assesses tumor response in terms of change in maximum axial dimensions in selected target lesions.

Furthermore, RECIST criteria may not be sufficient for metastatic tumor types such as ASPS, which frequently presents with extensive, highly vascular metastatic pulmonary lesions [32]. These metastatic lesions show subjective response on CT associated with reduced density and vascular/arterial perfusion (hypoattenuation) without the expected corresponding size reduction. This disproportional size reduction relative to clinical outcome may be a function of anti-angiogenic treatments, which may cause response via reduction of blood flow and necrosis in tumor that is not accounted for with current size-based tumor response criteria (Figure 3).

Recent studies in metastatic cancer imaging have demonstrated the added value of accounting for tumor density and volume using Size and Attenuation CT (SACT) [33], Mass, Attenuation, Size, and Structure (MASS) [34], or modified versions of the original Choi CT response criteria [35] beyond the axial dimensions provided by RECIST. In collaboration with investigators from the Department of Radiology and Imaging Sciences, we propose a more comprehensive tumor response method, Total Volume of Viable Tumor (TVVT), to quantify change in viable versus necrotic tumor volumes across all lesions through volumetric characterization of density distribution throughout all parts of all measurable tumors.

[figure not shown]

Figure 3A: Histograms can be used to calculate volumetric shifts in tumor composition and differentiate between necrotic and viable areas. Such use of thresholding can exclude areas not representative of tissues of interest (e.g., by excluding values over 100 Hounsfield units (HU) for calcifications and under -50HU for fat and artifact) giving a more comprehensive overall picture of tumor burden shift. **B:** Theoretical graphic representation of tumor trajectory over time in a

responding patient, demonstrating a more drastic decrease in TVVT (Total Volume of Viable Tumor, or volumetric HU) than axial dimensions on select lesions (RECIST); steeper declines may reflect treatment efficacy earlier than with RECIST.

In this retrospective pilot study, RECIST imaging measurements from 20 consecutive off-study patients will be compared to volumetric density (TVVT) CT measurements. The objective is to establish whether volumetric density/percent necrosis algorithms such as TVVT more accurately assess tumor response to treatment. No patient-related decisions will be made based on this assessment; applicable patients, who are all off study, will not be reconsented for retrospective data analysis.

3 Patient Selection

The adult cohort met study objectives and was closed to accrual with Amendment K, 02/01/13.

3.1 Eligibility Criteria

- Patients must have histologically confirmed alveolar soft part sarcoma. Pathology should be confirmed at the Laboratory of Pathology, National Institutes of Health.
- Patients must have measurable disease, defined as at least one lesion that can be accurately measured in at least one dimension (longest diameter to be recorded) as ≥ 20 mm with conventional techniques or as ≥ 10 mm with spiral CT scan. See Section 11 for the evaluation of measurable disease.
- Patients must have metastatic alveolar soft part sarcoma that is not curable by surgery. Patients who have surgically resectable tumors with metastasis will be considered on a case-by-case basis.
- Any prior therapy must have been completed ≥ 4 weeks prior to enrollment on protocol and the participant must have recovered to eligibility levels from prior toxicity. Patients should be at least 6 weeks out from nitrosoureas and mitomycin C. Prior radiation should have been completed ≥ 4 weeks prior to study enrollment and all associated toxicities resolved to eligibility levels. Patients must be ≥ 2 weeks since any investigational agent administered as part of a Phase 0 study (also referred to as an “early Phase I study” or “pre-Phase I study” where a sub-therapeutic dose of drug is administered) at the PI’s discretion, and should have recovered to eligibility levels from any toxicities.
- Any degree of prior treatment is allowed, including other anti-angiogenic treatments (e.g., VEGFR2 inhibitors or bevacizumab). Patients with no prior therapy are eligible, provided they have metastatic disease that is not curable by surgery.
- BSA ≥ 1.04 m².
- ECOG performance status ≤ 2 for adults, Karnofsky performance status $\geq 50\%$ for pediatric patients > 10 years of age, and Lansky performance status ≥ 50 for pediatric patients ≤ 10 years of age (Appendix A).
- Life expectancy of greater than 8 weeks.
- Patients must have normal organ and marrow function as defined below:

- absolute neutrophil count	$\geq 1,500/\text{mcL}$
- platelets	$\geq 100,000/\text{mcL}$
- total bilirubin	$< 1.5 \times \text{institutional upper limit of normal}$
- AST(SGOT)/ALT(SGPT)	$\leq 2.5 \times \text{institutional upper limit of normal}$
- creatinine	within normal limits based on age as follows:
	Age (Years) Maximum Serum Creatinine (mg/dL)
	≤ 5 0.8
	$5 < \text{age} \leq 10$ 1.0
	$10 < \text{age} \leq 15$ 1.2
	> 15 1.5

OR

- creatinine clearance $\geq 60 \text{ mL/min}$ for adults or $\geq 60 \text{ mL/min}/1.73\text{m}^2$ for children with creatinine levels above institutional limit of normal.

- QTc must be < 500 msec.
- Pediatric patients: Normal left ventricular function with ejection fraction $> 55\%$ or shortening fraction $\geq 27\%$.
- At present, the potential of AZD2171 for clinically significant drug interactions involving the CYP isozymes is unknown. However, studies of the agent in rats indicated possible suppression of CYP1A that may be of biological significance. Eligibility of patients receiving any medications or substances known to affect or with the potential to affect the activity of PK of AZD2171 will be determined following review of their case by the Principal Investigator. Efforts should be made to switch patients with brain metastases who are taking enzyme-inducing anticonvulsant agents (Appendix B) to other medications one week prior to starting therapy.
- AZD2171 has been shown to terminate fetal development in the rat, as expected for a process dependent on VEGF signaling. For this reason, women of child-bearing potential must have a negative pregnancy test prior to study entry. Women of child-bearing potential and men must agree to use adequate contraception (hormonal or barrier method of birth control; abstinence) prior to study entry and for the duration of study participation. Should a woman become pregnant or suspect she is pregnant while participating in this study, she should inform her treating physician immediately.
- Ability to understand and the willingness to sign a written informed consent document.
- Patients should not be receiving any other investigational agents.
- Prior therapy with anti-angiogenic agents is permitted.

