5.5 Duration of Follow-up

Patients will be followed for 30 days after the last dose is administered or until one of the following occurs: patient enrolls on another protocol, patient receives standard of care, or death, whichever comes first. The follow-up will consist of a phone call between Days 27-30 after the last dose to evaluate adverse events that were ongoing and any new events that might be deemed related to the therapy. Unacceptable toxicities (i.e., AEs related to the intervention) that have not resolved by Day 30 post-treatment will be followed via biweekly phone calls until stabilization or resolution.

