In vitro studies using hepatic cultures show that cediranib (AZD2171) did not inhibit CYP 1A2, 2A6, 2C8, 2C9, 2C19 and 2E1 and showed no induction of CYP 1A2, 2B6 and 3A4/5. It did weakly inhibit CYP 2D6 and 3A4/5, but this inhibition not expected to cause any clinically relevant drug interactions. The possibility that cediranib (AZD2171) may induce gastrointestinal CYP3A and UDPGT enzymes cannot be excluded; therefore the efficacy of hormonal contraceptives may be reduced. Advise women study participants to use an additional non-hormonal contraceptive method.

In vitro studies show that cediranib (AZD2171) is a weak inhibitor of BCRP, P-gp, OATP1B1, OATP1B3, OCT2, MATE1, UGT isoforms 1A1, 1A4 and 2B7. Use caution in patients who are taking concomitant medications that are sensitive substrates although clinically relevant inhibition of any of these is considered unlikely. *In vivo* studies show that cediranib (AZD2171) could increase exposure of drugs like metformin by inhibiting renal tubular transporter MATE2-K, but this is thought to be infrequent and mild in severity. Cediranib is not an inhibitor of OAT1 or OAT3.

Cediranib (AZD2171) is approximately 95% bound to human plasma proteins, with human serum albumin and α 1-acid glycoprotein accounting for most of this binding. Use caution in patients taking concomitant medications with narrow therapeutic ranges that are also highly protein-bound.

Oral anticoagulants are not absolutely contraindicated during treatment with AZD2171 (cediranib); however, use cediranib (AZD2171) with caution and increase monitoring in patients while on study. Patients who receive VEGF inhibitors are at increased risk of bleeding and hemorrhage.

Patient Care Implications: Agents that inhibit VEGF signaling have the potential to affect wound healing. For patients already enrolled onto the protocol, the manufacturer recommends holding cediranib (AZD2171) for 2 weeks prior to surgery and restarting when the surgical wound is healed. Protocol exclusion criteria should include patients who have had major thoracic or abdominal surgery within 2 weeks prior to start of study or patients with any surgical incision that is not fully healed.

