Advise women study participants of reproductive potential to use effective contraception while receiving study treatment and for at least 6 weeks after the last dose of cediranib (AZD2171). The efficacy of hormonal contraceptives may be reduced while receiving cediranib and an additional non-hormonal method should be considered. Men study participants should use a condom while receiving cediranib and for at least one week after the last dose. Refer to the protocol document for specific guidance.

Toxicities: A list of the adverse events and potential risks associated with AZD2171 can be found in Section 7.1.

Availability: AZD2171 is an investigational agent supplied to investigators by the Division of Cancer Treatment and Diagnosis (DCTD), NCI.

Agent Ordering: NCI-supplied agents may be requested by the Principal Investigator (or their authorized designees) at each participating institution. Pharmaceutical Management Branch (PMB) policy requires that the agent be shipped directly to the institution where the patient is to be treated. PMB does not permit the transfer of agents between institutions (unless prior approval from PMB is obtained). The CTEP-assigned protocol number must be used for ordering all CTEP-supplied investigational agents. The responsible investigator must be registered with CTEP, DCTD through an annual submission of FDA Form 1572 (Statement of Investigator), Curriculum Vitae, Supplemental Investigator Data Form (IDF), and Financial Disclosure Form (FDF). If there are several investigators, CTEP-supplied investigational agents for the study should be ordered under the name of the principal investigator.

Active CTEP-registered investigators and investigator-designated shipping designees and ordering designees can submit agent requests through the PMB Online Agent Order Processing (OAOP) application (<https://eapps-ctep.nci.nih.gov/OAOP/pages/login.jspx>). Access to OAOP requires the establishment of a CTEP Identity and Access Management (IAM) account (<https://eapps-ctep.nci.nih.gov/iam/>) and the maintenance of an “active” account status and a “current” password. For questions about drug orders, transfers, returns, or accountability, call [contact] Monday through Friday between 8:30 am and 4:30 pm (ET) or e-mail [contact] any time.

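### Contraception rules differ: Section 3.1 accepts a hormonal method alone until participation ends, while Section 8 doubts hormonal efficacy, words its second-method advice two ways, and runs to at least 6 weeks after the last dose for women

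*Combined protocol and SAP*

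**What the plan says.** Section 3.1 (Eligibility Criteria) requires women of child-bearing potential and men to agree to "adequate contraception (hormonal or barrier method of birth control; abstinence) prior to study entry and for the duration of study participation". The methods are listed as alternatives. The criterion mentions no loss of hormonal efficacy, no second method and no period after the last dose.

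Section 8 (Pharmaceutical Information) takes up the subject twice:

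- Under potential drug interactions, it notes that the drug might induce gut enzymes and concludes: "therefore the efficacy of hormonal contraceptives may be reduced. Advise women study participants to use an additional non-hormonal contraceptive method".
- Under patient care implications, it asks for "women study participants of reproductive potential to use effective contraception while receiving study treatment and for at least 6 weeks after the last dose". It repeats the warning about hormonal methods, then says that "an additional non-hormonal method should be considered. Men study participants should use a condom while receiving cediranib and for at least one week after" dosing ends. It closes with "Refer to the protocol document for specific guidance".

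The length of participation comes from Sections 5.5 and 5.6. Section 5.5 says "Patients will be followed for 30 days after the last dose is administered or until one of the following occurs". The events that can cut this period short are listed as "patient enrolls on another protocol, patient receives standard of care, or death, whichever comes first". On the form of contact, the section states: "The follow-up will consist of a phone call between Days 27-30 after the last dose". Follow-up goes beyond day 30 only for unresolved toxicity related to the drug. Section 5.6 makes completion of the 30-day follow-up a reason for removal from study.

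**The concern.** Staff who take the rule from the list in Section 3.1 would ask less of women than Section 8 does, in two respects: whether a second method is used, and how long contraception continues after the last dose. Within Section 8 it is also unclear how strong the second-method advice is meant to be.

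This is a matter of participant safety. Section 3.1 gives harm to fetal development in rats as the reason for the rule, and Section 3.2 excludes pregnant women because of the drug's abortifacient effects. Sample size, error rates and the response analysis do not depend on it.

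**Working it through.** The plan gives no figure to reproduce. The check sets the passages side by side and does one subtraction.

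**Method and duration**

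| Point | Section 3.1 | Section 8, drug interactions | Section 8, patient care |
|---|---|---|---|
| Hormonal method alone | Accepted as one alternative | Efficacy may be reduced | Efficacy may be reduced |
| Second, non-hormonal method (women) | Not mentioned | Staff are to advise its use | To be considered |
| Men | Hormonal, barrier or abstinence | Not mentioned | Condom |
| Period after last dose, women | None beyond participation | Not mentioned | At least 6 weeks |
| Period after last dose, men | None beyond participation | Not mentioned | At least 1 week |

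The condom named for men is a barrier method, so Section 3.1 already accepts it. Section 8 narrows the choice for men but does not contradict it.

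**Gap in duration**

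Inputs: 6 weeks = 42 days for women and 1 week = 7 days for men (Section 8); participation normally ends at day 30 after the last dose (Sections 5.5 and 5.6).

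Women: gap = max(0, 42 − exit day).

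- Standard exit at day 30: 42 − 30 = 12 days.
- Exit at day 14, for example on entering another protocol (day 14 is an illustrative assumption): 42 − 14 = 28 days.
- Limiting case, exit on the day of the last dose: 42 days.
- Toxicity follow-up to day 42 or later: 0 days. If the biweekly calls are two weeks apart and counted from the day 27–30 call (an assumption, since Section 5.5 gives no date for the first one), that call falls between 27 + 14 = day 41 and 30 + 14 = day 44, leaving a gap of 1 to 0 days.

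Men: gap = max(0, 7 − exit day). Exit at day 30 gives 0. A gap arises only with exit before day 7, and is at most 7 days.

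**Is there a tie-breaker?**

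The only candidate is the closing sentence of the contraception advice in Section 8, which sends the reader to the protocol document. Section 8 is itself part of the protocol, and the sentence names no section and no order of precedence. The only other list of accepted methods in the supplied text is Section 3.1, which covers neither a second method nor the period after the last dose. The cross-reference therefore leaves both points open.

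**Who is affected**

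Section 2.4 reports accrual closed and three patients still on drug: two pediatric patients and one adult. Sex and current age are not given, so the number affected is between 0 and 3. The pediatric patients had received 59 and 84 cycles. At 28 days per cycle that is 59 × 28 = 1,652 days (about 4.5 years) and 84 × 28 = 2,352 days (about 6.4 years), so patients who entered under 16 may since have reached reproductive age.

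**The case against.** The best counter-argument is that the texts add to each other and do not conflict. Section 3.1 is an entry criterion that sets a minimum. Section 8 gives agent-specific advice for participants on treatment and already contains the fuller content. Nothing says that a second method is unnecessary or that contraception may stop at day 30. With accrual closed, nobody new is screened against Section 3.1, and the text addressed to the remaining patients is Section 8. The two wordings in Section 8 are both advisory and point the same way. The consent pages and Appendix D, where patients are probably counselled, were not supplied. Section 7.2.2.3 also requires any pregnancy up to 90 days after the last dose to be reported, which spans the whole 42-day period.

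Much of this stands. The sections can be followed together, the difference in wording within Section 8 is one of strength, the practical reach is small, and nothing can be said about what patients are actually told. Three points remain:

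- Section 3.1 sets its own period, through the end of participation, so it reads as an on-study rule as well as an entry screen. Followed alone, it asks for less.
- The 90-day provision concerns reporting and outcome follow-up. It does not set a contraception period, and the one routine contact in Section 5.5 falls on days 27–30.
- The cross-reference in Section 8 does not settle what Section 3.1 leaves out.

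**Conclusion.** The concern holds as a minor inconsistency. Section 3.1 and Section 8 differ on whether a hormonal method alone is enough and on how long contraception continues for women, and Section 8 words its second-method advice in two strengths. For women the difference in duration is 12 days in the standard case. This assumes that study participation, which the protocol does not define, ends with removal from study at day 30. The gap is wider with earlier exit and disappears if toxicity follow-up reaches day 42. For men there is no gap in duration in the standard case.

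Between 0 and 3 patients are affected, and no endpoint or analysis is. The conclusion is limited to the supplied text. It does not say which contraception rule is right.

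**What to change.** Reconcile the contraception criterion in Section 3.1 with the two statements in Section 8 (drug interactions and patient care implications) so that all three say the same thing on accepted methods, on whether a second method is required or only advised, and on duration after the last dose for women and for men. Replace the open cross-reference in Section 8 with a pointer to the section that governs. The clinical team should choose the content, check it against the consent form and Appendix D, and tell the patients still on drug if the requirement changes.

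The cost is wording in three places, that check, and notice to at most three patients. Whether the consent form or Appendix D needs a change cannot be judged from the supplied text.
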